As the facial surface mesh is made up of thousands of points, an overall mean value for the error is often reported. If one facial surface mesh is totally in front of the other, all the distance measurements will be either positive or negative and therefore the mean is valid. If however some parts of one mesh lie behind and some in front of the other mesh, distance measurements for the whole face will be made up of positive and negative values. Any positive values will cancel out any negative values under-estimating the mean difference and so biasing the results. In order to overcome this problem, some studies use the absolute mean values or Euclidean distances, which ignore the sign (direction) and report on the magnitude of error or the RMS error. The RMS error is derived from all the points making up the surface mesh which makes it not clinically useful, as the site of the error remains unknown; however, dividing the face into anatomical regions and analyzing them separately immediately focuses on

the areas of error. Many studies assess the accuracy of the prediction by comparing the differences in distance between the prediction and the actual surfaces using the entire face, including the areas that have been used for alignment, i.e. the areas with minimal change. Therefore a large percentage of the mesh has minimal or no change; this will bias the accuracy by reducing the impact of the error—the data will be skewed towards the smaller values. In order to overcome this, areas of the face used for alignment can be excluded and the remaining mesh divided into anatomically relevant regions this method highlights the true level of error in the predictive ability of the package.

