For long time, the analysis of three-dimensional (3D) facial images has generally been limited to linear and angular measurements between anatomical landmarks. The operator usually identifies and digitizes a set of landmarks that result in a 3D landmark configuration, which is then used for analysis. The limited number of accurately identifiable landmarks does not allow a comprehensive analysis of the facial morphology. To overcome this problem, the concept of a ‘generic mesh’ was introduced.(53) The presented innovative approach provides a useful tool for 3D analysis of the face; it provides comprehensive evaluation of the morphological characteristics, which is superior to assessment at a limited set of individual landmarks. A generic mesh can be thought of as a ‘simplified symmetrized facial mask’ that contains a known number and distribution of points or ‘vertices’. The triangles or ‘faces’ formed by these vertices are indexed or ordered within the file structure. The generic mesh can be used to standardize the number and distribution of vertices for images of the same individual and between individuals. Using the process of ‘conformation’, the generic facial mesh can be ‘wrapped’ around any facial image depending on several anchoring landmarks, whilst the remaining points are

mathematically fitted or elastically deformed to maintain the surface topography of the original 3D image. The conformation process on the preoperative and postoperative 3D facial images produces two meshes, which have the same number of vertices and triangles. Each vertex represents a corresponding point on the pre- and post-operative conformed meshes. The accuracy of the conformation process of the generic facial meshes will determine the precision in relating the corresponding facial points for the analysis.

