### ***Sample size calculation***

Based upon the assumption that we need to reach 90% accuracy, in light of the results of Resnick CM et al (2016), the computed effect size for the accuracy of linear measurements was found to be (1.05), using alpha ( $\alpha$ ) level of (5%) and Beta ( $\beta$ ) level of (20%) i.e. power = 80%; the study will include 10 subjects. To compensate for 15% for the use of non-parametric tests; the final minimum estimated sample size will be 12 subjects. Sample size calculation was performed using G\*Power Version 3.1.9.2.

Patients to be included:

- a) Patients who have class III facial deformity to be corrected using bimaxillary orthognathic surgery.
- b) No medical problems that might interfere with general anesthesia or interfere with bone and soft tissue healing.

Patients will be excluded if:

- a) There are craniofacial anomalies including cleft lip/palate,
- b) Patient have previous maxillofacial operations or facial scars,
- c) Correction mandates multi-segment Le Fort I osteotomies,
- d) There are orthodontic appliances in place at the time of T1 records.
- e) Genioplasty is recommended for deformity correction.
- f) There is facial Asymmetry.

All the patients are consented for using their data in research purposes.

The CBCT scans of class III patients who undergone maxillary advancement with minimal or without impaction and mandibular setback will be identified. The preoperative and 6 months postoperative CBCT images will be anonymized and will be saved in a password protected computer. Only the research team members will have access to the research data.

In order to quantify the actual amount of surgical movement, the pre and post-operation CBCT voxel based super imposition using ONDEMAND 3d. The surgical movement will be quantified using direct slice land-marking.

Using the pre-operation CBCT to do the surgical mock up and the soft tissue simulation on dolphin 3D. Soft tissue surface models of the simulation and the actual postoperative images will be generated and exported as STLs.

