### **Data Analysis**

Superimposition of the predicted and the post-operative STLs and conformation of the generic meshes will be performed. Using VR mesh software, the mesh will be segmented into pre-identified anatomical regions. The distance between the corresponding vertices will be displayed

as a colour scale in milli-meter and will be analyzed in the individual dimension of space (x, y and z) using in-house software developed for this purpose and each dimension will be displayed as a colour coded distance map. It will be generated to illustrate the magnitude and anatomical regions with prediction inaccuracies analysis. Using this software, the minimum, maximum, mean, standard deviation (SD), absolute maximum, absolute mean, and absolute SD of 90% of the points of each facial anatomical region will be measured.

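### With no left/right sign convention, the signed x mean of a region spanning the midline cannot show a symmetric width error, and the planned regional statistics do not tell too wide from too narrow

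*Combined protocol and SAP*

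**What the plan says.** Data Analysis superimposes the predicted and actual surfaces, conforms a generic mesh to each and divides the mesh into anatomical regions. The regions are said to be fixed in advance but are not listed. Vertex distances "will be analyzed in the individual dimension of space (x, y and z) using in-house software developed for this purpose", with a colour map for each axis. For 90% of the points in each region, the plan reports the signed mean, SD, minimum and maximum, and the mean, SD and maximum of the absolute distances. How the 90% are chosen is not stated, and neither is any rule for the sign of x on the left and right sides.

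Four other places bear on this:

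- The exclusion list under Sample size calculation removes a patient if "There is facial Asymmetry".
- The background on comparing pre- and post-operative analyses says that the signed difference takes account of direction and the absolute difference does not.
- The background on image registration warns of signed means: "Any positive values will cancel out any negative values under-estimating the mean difference and so biasing the results". It gives absolute or RMS values as the usual remedy.
- The background on dense correspondence describes the generic mesh as a "simplified symmetrized facial mask".

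Statistical analysis plans a paired t-test or Wilcoxon signed-rank test of actual against software measurement. It does not say which summary, axis or region supplies that measurement.

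**The concern.** The signed mean is the planned summary that is meant to carry direction. For y and z it does so, because a forward or downward error usually has the same sign on both sides of the face. For x it does not. If the software makes a midline structure too wide, the error points right on the right side and left on the left side, and the two halves offset each other. Nose, lips and chin are the likely candidates for such regions.

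The absolute mean restores the size of the error but gives the same value for too wide and too narrow. A systematic tendency to predict, say, too broad a nose would therefore be visible as inaccuracy of unknown direction. If the signed x measurement were also the tested variable, the stated hypothesis of no difference would tend to survive whatever the width error, and more patients would not change that.

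**Working it through.** **The plan's own figure.** The only computed figure is the sample size: "the computed effect size for the accuracy of linear measurements was found to be (1.05"), alpha 5%, power 80%. Exact noncentral-t power for a paired t-test, two-sided (sidedness is not stated), is 78.7% at n = 9 and 83.9% at n = 10, so 10 reproduces. The plan continues: "To compensate for 15% for the use of non-parametric tests; the final minimum estimated sample size will be 12 subjects". Since 10 × 1.15 = 11.5 and 10 / 0.85 = 11.8, 12 reproduces too. The present point does not dispute it; n = 12 is used below.

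**Inputs that are assumed.** The documents give no error sizes, error shapes or between-patient SDs for x. All of those below are illustrative.

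**Step 1: one patient, undivided midline region.** Let u run from -1 (left edge) to +1 (right edge), with vertices spread evenly and total width error e. For an error growing linearly from the midline, d(u) = (e/2)u. Keep the 90% of points with the smallest absolute error, so |u| ≤ 0.9.

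- Signed mean: the average of (e/2)u over a symmetric interval = 0.00 mm for e = 1, 2 and 4.
- Absolute mean: (e/2) × 0.45 = 0.23, 0.45 and 0.90 mm.
- For e = 2: SD = 0.9/√3 = 0.52 mm, minimum/maximum -0.90/+0.90 mm, absolute maximum 0.90 mm.
- If the error is instead constant on each side, the signed mean is still 0.00 mm and the absolute mean is e/2 = 0.5, 1.0 and 2.0 mm.

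**Step 2: too wide against too narrow.** Compare an error of +2 mm at each edge with one of -2 mm at each edge (linear, same 90%).

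| Regional x statistic (mm) | Too wide | Too narrow |
|---|---|---|
| Minimum / maximum | -1.8 / +1.8 | -1.8 / +1.8 |
| Signed mean | 0.00 | 0.00 |
| SD | 1.04 | 1.04 |
| Absolute maximum | 1.8 | 1.8 |
| Absolute mean | 0.90 | 0.90 |
| Absolute SD | 0.52 | 0.52 |
| Lateral-positive mean (not planned) | +0.90 | -0.90 |

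All seven planned statistics coincide, because the two errors produce the same set of vertex values with the sides exchanged.

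**Step 3: imperfect symmetry and other trimming.** Let the right side's error be a fraction r of the left's, with e = 2 and all points kept. The signed mean is (-0.5 + 0.5r)/2, which is -0.05 mm for r = 0.8 and -0.125 mm for r = 0.5. Cancellation is then incomplete, but what remains reflects the left-right imbalance, not the width error. Too wide with the left side worse gives the same values as too narrow with the right side worse. If the trimming instead dropped the top 10% of signed values, u would run from -1 to 0.8 and the signed mean for e = 2 would be -0.10 mm. By the argument of Step 2, it would be the same in both directions.

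**Step 4: a test at n = 12, if it used the signed x measurement.** Let patient i have error s_i·x/18 + t_i for x from -18 to +18 mm (all points kept). The edge error s_i is N(w, 1) and the lateral drift t_i is N(0, 0.3), in mm with SDs as second arguments.

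- The signed regional mean is t_i. It does not contain s_i, so the test rejects at its 5% level for every w. Simulation of 4,000 trials gave 4.5% (w = 1) and 5.3% (w = 2).
- The lateral-positive mean is s_i/2: the drift cancels, the mean is w/2 and the SD is 0.5, so the standardised effect is w. Noncentral-t power at n = 12 is 88% for w = 1 and above 99.9% for w = 2. The simulation gave 87.5% and 100%.
- The absolute mean averaged 1.049 mm for w = +2 and 1.050 mm for w = -2. Tested against zero it rejected in 100% of trials even at w = 0, so it cannot stand in as a test of width bias.

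A second model used a mean total width error of 2 mm and independent left and right variation of SD 0.3 mm. The signed x mean was rejected in 4.9% of 5,000 runs.

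**The case against.** The strongest reply is that the plan already knows about cancellation and provides for it. The background warns of it, names absolute values as the remedy, and Data Analysis adopts them. For the mirror-image error in Step 1, only one of the seven summaries is zero; the other six and the x colour map register it. The stated aim is accuracy, and the maps are meant to show how large the errors are and where they lie. Direction of width error is not a declared objective. All of this stands as regards magnitude. It does not supply direction: the colour map might show it to the eye, but the plan does not say that the map is signed and derives no width statistic from it.

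A reader might infer that a mis-predicted width shows as zero error in this study. The documents do not support that, because the absolute summaries, SD and range are all planned. A reader might also infer that the planned test will report no difference in width. That too goes beyond the text, since Statistical analysis never names the signed x mean as the tested variable.

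Three further limits stand. The regions are not listed, so undivided midline regions are an inference. If nose, lips and chin are split at the midline, each half keeps its sign, though the halves still need a sign reversal before pooling. Excluding patients with asymmetric faces does not make the prediction error symmetric, so cancellation is approximate. And the summaries use 90% of the points by an unstated rule, which can leave a small residual mean.

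**Conclusion.** The point holds in a limited form. In any region spanning the midline, the signed x mean is close to uninformative about a roughly symmetric width error, and the planned regional statistics do not separate too wide from too narrow. What is lost is transverse direction, not magnitude.

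For an assumed total width error of 2 mm, the signed x mean is 0.00 mm under exact symmetry. It is about -0.05 to -0.13 mm when one side's error is 80% or 50% of the other's, against an absolute mean of 0.45 mm in the symmetric linear case. The loss of power (about 5% against 87% to 100%) applies only if the signed regional x measurement is what the paired test uses, and it rests on assumed error sizes, a linear shape and assumed SDs. The geometry does not depend on those assumptions; the figures do. The correction is worth making because the signed mean is the planned summary that should carry direction, and for x it needs a sign convention to do so.

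**What to change.** In Data Analysis, define the x difference as lateral-positive on both sides: reverse its sign for vertices on one side of the mid-sagittal plane before computing signed regional statistics. Because the generic mesh is symmetrised, the side of each vertex should be identifiable. Report the result as the signed x (width) error for each region, alongside the absolute x mean. Keep the plain signed x mean only as a check for lateral shift of a whole region, and state that it is not evidence of transverse accuracy.

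List the regions, and say which span the midline and how the 90% of points are chosen. In Statistical analysis, name the summary that enters the paired test; the sign convention alone does not settle that.

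The cost is one sign change in the in-house software, one extra reported statistic and a few sentences in the plan. No new scans or patients are needed.

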### ***Study Hypothesis***

There will be no difference between actual soft tissue results and Dolphin 3D software soft tissue prediction.

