### ***Statistical analysis***

Numerical data will be explored for normality by checking the distribution of data and using tests of normality (Kolmogorov-Smirnov and Shapiro-Wilk tests). Data will be presented as mean, median, standard deviation (SD), minimum, maximum and 95% Confidence Interval (95% CI) for the mean values. For parametric data, paired t-test will be used to compare between actual soft tissue measurement and software measurement. For non-parametric data, Wilcoxon signed-rank test will be used to compare between actual soft tissue measurement and software measurement. Inter- and intra-examiner reliability will be assessed using Cronbach's alpha and Intra-Class Correlation coefficients.

The significance level will be set at  $P \leq 0.05$ . Statistical analysis will be performed with IBM® SPSS® Statistics Version 20 for Windows.

---

\* IBM Corporation, NY, USA.

\* SPSS, Inc., an IBM Company.

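### One global hypothesis and a sample size for one comparison, but several regions, three axes and seven summaries, with no primary endpoint or rule for a verdict

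*Combined protocol and SAP*

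**What the plan says.** The Study Hypothesis section makes one global statement: "There will be no difference between actual soft tissue results and Dolphin 3D software soft tissue prediction". It names no region, axis or summary measure.

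The Sample size calculation section rests on one effect size ("the computed effect size for the accuracy of linear measurements was found to be (1.05")), a 5% alpha that is not divided, and 80% power: "i.e. power = 80%; the study will include 10 subjects". The number then rises to 12, for this reason: "To compensate for 15% for the use of non-parametric tests". Multiplicity is not mentioned.

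The Data Analysis section divides the face into several regions fixed in advance but does not give their number. It says that vertex distances "will be analyzed in the individual dimension of space (x, y and z"), with a colour map for each axis. For each region it lists seven summaries: minimum, maximum, mean, SD, absolute maximum, absolute mean and absolute SD, each over 90% of the points.

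The Statistical analysis section plans a paired t-test or a Wilcoxon signed-rank test of actual against software measurement, and 95% CIs for means. "The significance level will be set at" P ≤ 0.05. It does not say which summary is tested, whether tests are run by region or by axis, or which result decides the hypothesis.

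**The concern.** The plan asks one question, is sized for one test, and produces many candidate answers. Two consequences follow.

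- **Error rate.** If each region and axis gets its own test at 0.05, the chance of at least one false rejection of the global hypothesis exceeds 5% by an amount that the plan neither states nor controls. The 80% power figure does not describe that family of tests.
- **Choice of summary.** Signed and absolute summaries of the same faces can point in opposite directions. With none chosen beforehand, the conclusion about the software could depend on which one is emphasised after the data are seen.

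The study exists to give a verdict on accuracy, so a plan that can support either verdict weakens its main output.

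**Working it through.** **1. Reproduce the plan's sample size.** Inputs from the Sample size calculation section: d = 1.05, alpha = 0.05, power = 80%. Sidedness is not stated. Power of a two-sided paired t-test comes from the noncentral t distribution with n − 1 degrees of freedom and noncentrality d√n.

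- n = 9: noncentrality 3.15, power 0.787
- n = 10: noncentrality 1.05 × √10 = 3.32, power 0.839
- n = 12: noncentrality 1.05 × √12 = 3.64, power 0.911

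The smallest n that reaches 80% is 10, as stated. A one-sided test would need 8, and two independent groups would need 16 per group. Then 10 × 1.15 = 11.5, rounded up to 12. The stated figure is therefore that of one two-sided paired test at 5%, and the 15% is already used for the non-parametric option.

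**2. Family-wise error if signed means are tested by region and axis.** The number of regions R is not given; R = 2 to 10 is assumed. The number of tests is k = 3R, each at 0.05, with n = 12 and no true difference. For independent tests the formula is 1 − 0.95^k. For correlated tests, one-sample t-tests on equicorrelated normal data were simulated (200,000 replicates per case). The correlations are assumptions.

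| Regions | Tests k | Independent | Correlation 0.5 | Correlation 0.8 |
|---|---|---|---|---|
| 2 | 6 | 1 − 0.95^6 = 26% | 21% | 15% |
| 5 | 15 | 1 − 0.95^15 = 54% | 38% | 22% |
| 10 | 30 | 1 − 0.95^30 = 79% | 54% | 28% |

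Across the table the rate is about 3 to 16 times the nominal 5% (15/5 = 3; 79/5 ≈ 16). It passes 50% from 14 independent tests (1 − 0.95^14 = 51%), that is, from 5 regions by 3 axes. At correlation 0.5 it does so only at about 9 to 10 regions.

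**3. Choice of summary.** This step needs no assumption about R or correlation.

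- Absolute mean and absolute maximum distances are positive for every patient. Tested against zero by Wilcoxon with n = 12, all ranks carry the same sign and the two-sided exact P is 2/2^12 = 2/4096 ≈ 0.0005, whatever the size of the error in millimetres.
- Signed means of the same data can be near zero because positive and negative distances offset each other. The plan's own review makes this point under Comparing pre-operative and post-operative analyses and again under Analysis based on surface meshes.

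So even with one region, the same 12 patients could give P ≈ 0.0005 on one listed summary and a non-significant result on another.

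**The case against.** The strongest reply is that the Data Analysis section describes measurement and mapping, not testing. Its sentence on regional summaries does not mention axes, and the Statistical analysis section mentions neither regions nor axes. A reader might infer that the plan commits to a separate 0.05 test for every region and axis. The documents do not say so, and the rates in step 2 hold only under that reading. The reply does not remove the gap, because the unit of testing is then undefined.

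A reader might also infer that a false rejection is likely, or a mix of significant and non-significant regions almost certain. Neither follows. Both depend on the number of regions and their correlation, which are not given. Regions of one face share the same superimposition, so independence is the least plausible case, and at correlation 0.8 the rate stays below 30% even with 10 regions. If true errors differ by region, a mixed result is information that the study seeks.

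Three further points stand:

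- The zero-mean simulation fits signed means only. An error rate under a zero null has no meaning for absolute distances.
- The regions are fixed in advance, so free choice of regions afterwards is not supported. Choice among summaries remains open.
- A single pooled figure hides where the error lies, which the plan's own review criticises for whole-mesh measures. Regional results must therefore stay in the report.

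**Conclusion.** The concern holds in a limited form. The plan has one global hypothesis, a sample size for one two-sided paired test, several regions, three axes and seven summaries, and neither a primary endpoint nor a rule for reaching one verdict.

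Under the inferred reading, family-wise error is uncontrolled: somewhere between about 15% and 79% for an assumed 2 to 10 regions with 12 patients, with the lower part of that range more plausible because regions of one face are correlated. The dependence of the verdict on signed or absolute summaries needs neither assumption and is the firmer half of the point. It requires only that an absolute summary be tested against zero, which the plan leaves open. A related gap is that the measurements are distances, which are already differences, while the planned test compares two measurements, so the tested variable itself needs a definition.

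**What to change.** Before analysis, make these changes:

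1. Name one primary endpoint. An example is each patient's mean Euclidean distance between corresponding vertices over a pre-named set of operated regions, leaving out the area used for alignment.
2. Report it with its 95% CI against an accuracy limit stated in advance and justified for soft tissue. The 2 mm level cited under 3D Virtual planning and prediction comes from 3D planning studies and would need that justification.
3. Present region-by-axis signed and absolute results as estimates with 95% CIs and no claims of significance. This keeps the information on where errors lie.
4. State that the 80% power figure refers to a single paired comparison. The effect size of 1.05 was not computed for a Euclidean mean against a limit, so recalculate power or expected CI width for the new endpoint at 12 patients.

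A multiplicity correction of difference tests is a poor substitute. With Bonferroni, power at 12 patients and d = 1.05 falls from 91% to 66% (6 tests), 50% (15) or 38% (30), and lower power makes a finding of no difference easier to reach.

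The cost is revised wording, one justified limit and one recalculation. The wording changes themselves call for no new scans; whether 12 patients suffice for the new endpoint depends on the recalculation. The downside is that regional P-values lose confirmatory status.
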